**CONFIDENTIAL**  
 Project No. BLI-1005-002  
 Statistical Analysis Plan for PDC-1421

“Final” Page 10 of 34  
 Protocol Version: 2.3  
 SAP Version: 20180626\_01

Page	Before version : 1.4	Page	Content after modification Version : 1.5
14	None	14	
1.2.4.4 13-week Repeated Dose Subchronic Toxicity Study in Rats  To evaluate the subchronic toxicity of PDC-1421, four groups of rats were administered with 0, 750, 1500 and 2500 mg/kg/once daily p.o. for 13 weeks (90 days). There are no treatment-related mortality, clinical signs of toxicity and ophthalmologic abnormality in the study. And no significant toxicity evidences in mean body weights, mean body weight gains and food consumption in all treatment groups were noted. In clinical pathology, no toxicity evidences were noted for all parameters (hematology, serum chemistry and urinalysis), no treatment-related gross abnormality was found at necropsy, and no significant toxicity evidences in organ weights evaluation. And the histopathological findings showed that no treatment-related changes in vehicle control and PDC-1421 treated groups. It was estimated that the NOAEL of PDC-1421 of the 13-week repeated dose toxicity study is 2500 mg/kg/day for both males and females.

22	As Page 2	22	As Page 2
24	3.5.4 Dosing Regimen, packing and labeling Table 14. Summary of dosing regimen Visits of Part II Biweekly for 28 days	24	3.5.4 Dosing Regimen, packing and labeling Table 14. Summary of dosing regimen Visits of Part II Biweekly for 42 days
25	In part II, eligible subjects are randomized into one of three treatment arms in a 1:1:1 ratio [one capsule of PDC-1421 Capsule and placebo thrice daily; two capsules of PDC-1421 Capsule thrice daily; two capsules of placebo thrice daily] for 28 days. After the two weeks of drug administration,		In part II, eligible subjects are randomized into one of three treatment arms in a 1:1:1 ratio [one capsule of PDC-1421 Capsule and placebo thrice daily; two capsules of PDC-1421 Capsule thrice daily; two capsules of placebo thrice daily] for 42 days. After the two weeks of drug

Page	Before version : 1.4	Page	Content after modification Version : 1.5
	
subjects will return to the center for assessments then get another study drug bag for the following 14 days. The biweekly clinic visits are two times and one week later after the last dose for follow-up.
 
Investigational drug (PDC-1421 Capsule or placebo) are provided by BioLite, Inc. and stored in Department of Pharmacy, Taipei Veterans General Hospital, Linkou Chang Gung Memorial Hospital and Taipei City Hospital, Songde Branch. In part I, the first six subjects will take 21 packs with 21 capsules of PDC-1421 Capsule and another six take 21 packs with 42 capsules of PDC-1421 Capsule in every week of trial.
 
In part II, subjects will be dispensed with study drug per 2 weeks which are packaged in a drug bag. A drug bag will contain 42 packs. Depending on the study arms, each pack may contain 2 PDC-1421 Capsules, 2 placebos or 1 PDC-1421 Capsule plus 1 placebo. Each subject will be administered 84 packs in the end of trial. The drug bag of investigational drug is clearly labeled as following
		
administration, subjects will return to the center for assessments then get another study drug bag for the following 14 days. The biweekly clinic visits are three times and one week later after the last dose for follow-up.
 
Investigational drug (PDC-1421 Capsule or placebo) are provided by BioLite, Inc. and stored in Department of Pharmacy, Taipei Veterans General Hospital, Linkou Chang Gung Memorial Hospital, Taipei City Hospital, Songde Branch and Tri-Service General Hospital, Neihu Main Facility and Tingjhou Branch. In part I, the first six subjects will take 21 packs with 21 capsules of PDC-1421 Capsule and another six take 21 packs with 42 capsules of PDC-1421 Capsule in every week of trial. In part II, subjects will be dispensed with study drug per 2 weeks which are packaged in a drug bag. A drug bag will contain 42 packs. Depending on the study arms, each pack may contain 2 PDC-1421 Capsules, 2 placebos or 1 PDC-1421 Capsule plus 1 placebo. Each subject will be administered 126 packs in the end of trial.
 
The drug bag of investigational drug is clearly labeled as following

32	
4.4.2 Subject Number Allocation
 
The second digit: the site number; Taipei Veterans General Hospital will be assigned to “1”, Linkou Chang Gung Memorial Hospital will be assigned to “2” and Taipei City Hospital, Songde Branch will be assigned to “3”.
	32	
4.4.2 Subject Number Allocation
 
The second digit: the site number; Taipei Veterans General Hospital will be assigned to “1”, Linkou Chang Gung Memorial Hospital will be assigned to “2” and Taipei City Hospital, Songde Branch will be assigned to “3”, Tri-Service General Hospital, Neihu Main Facility will be assigned to “4”. Tri-Service General Hospital, Tingjhou Branch will be assigned to “5”.

Page	Before version : 1.4	Page	Content after modification Version : 1.5
52	
10.4 Institutional Review Board (IRB)
 
This study is conducted to be consistent with the principles of the Declaration of Helsinki and GCP. This protocol and any supplementary documents, including written informed consent form, subject recruitment advertisements and Investigator's Brochure, must be reviewed and approved by IRB of the Taipei Veterans General Hospital, Linkou Chang Gung Memorial Hospital and Taipei City Hospital, Songde Branch qualified with local legal prescriptions prior to study initiation...
	52	
10.4 Institutional Review Board (IRB)
 
This study is conducted to be consistent with the principles of the Declaration of Helsinki and GCP. This protocol and any supplementary documents, including written informed consent form, subject recruitment advertisements and Investigator's Brochure, must be reviewed and approved by IRB of the Taipei Veterans General Hospital, Linkou Chang Gung Memorial Hospital, Taipei City Hospital, Songde Branch and Tri-Service General Hospital qualified with local legal prescriptions prior to study initiation...

Page	Before version : 1.5	Page	Content after modification Version : 2.0
32	
4.4.2 Subject Number Allocation
 
The second digit: the site number; Taipei Veterans General Hospital will be assigned to “1”, Linkou Chang Gung Memorial Hospital will be assigned to “2” and Taipei City Hospital, Songde Branch will be assigned to “3”, Tri-Service General Hospital, Neihu Main Facility will be assigned to “4”. Tri-Service General Hospital, Tingzhou Branch will be assigned to “5”.
	32	
4.4.2 Subject Number Allocation
 
The second digit: the site number.

Page	Before version : 2.1	Page	Content after modification Version : 2.2
21	
3.1 General Design
 
The targeted population of this study is 72 subjects who met the per-protocol basis, in which 12 are assigned to part I, 60 are assigned to part II.
	21	
3.1 General Design
 
The targeted population of this study is 72 subjects who met the intent-to-treat (ITT) basis, in which 12 are assigned to part I, 60 are assigned to part II.

Page	Before version : 2.1	Page	Content after modification Version : 2.2
48	8.1 Sample Size Determination Based on our study design, it is planned to enroll 60 subjects who met the per-protocol basis.	48	8.1 Sample Size Determination Based on our study design, it is planned to enroll 60 subjects who met the intent-to-treat (ITT) basis.

Page	Before version : 2.2	Page	Content after modification Version : 2.3
42	The total score is used to define treatment response ( $\geq 40\%$ reduction from baseline) and partial response (20-39% reduction from baseline).	42	Percentage of partial responders (defined as a participant with a 25-50% decrease from baseline in total score) and responders (defined as a participant with $\geq 50\%$ decrease from baseline in total score).

## 5. INVESTIGATIONAL PLAN

### 5.1 Objective

#### 5.1.1 *Primary objective*

The primary objective of this trial was to determine the effective doses and treatment period of PDC-1421 Capsule in subjects with MDD.

#### 5.1.2 *Secondary objective*

[figure not shown]
To evaluate the safety of PDC-1421 Capsule in subjects receiving PDC-1421 at various dose levels .

### 5.2 Study Design

The screening phase is intended for diagnosing and assessing the patient for possible inclusion in the study and for providing an adequate washout period. The following study will be conducted in two parts. The targeted population of this study is 72 subjects who met the intent-to-treat (ITT) basis, in which 12 are assigned to part I, 60 are assigned to part II. Part I is an open-label study, multiple center and dose escalation evaluation in twelve patients. Six subjects each will be evaluated for any safety concerns at 1 or 2 capsules TID dose for 28 days, sequentially. Each of them will be assessed twice in the first week after administration of PDC-1421 Capsules and once a week in the following treatment. Part II is a randomized, double-blind, placebo-controlled, parallel-group study. 60 subjects will be randomly assigned on a 1:1:1 basis to one of the three treatment arms (1 PDC-1421 Capsule plus 1 placebo TID, 2 PDC-1421 Capsule TID, 2 placebo TID) for 6 weeks (42 days) and evaluated the safety and efficacy every two weeks during the treatment period. The performance of PDC-1421 Capsule on MDD subjects will provide us with valuable information for our next phase of the study.

### 5.2.1 Schematic Diagram of The Study:

[figure not shown]
#### Part I.

\* Subjects are assessed once between visit 2 and 4

→ Checkpoints

#### Part II.

### 5.2.2 *Study Medication Administration*

In part I, six subjects each will take 1 or 2 capsules thrice daily for 28 days, sequentially. Subjects are assessed twice in the first week after drug administration and they will receive the study drug bag for the following 7 days every week. In part II, eligible subjects are randomized into one of three treatment arms in a 1:1:1 ratio (one capsule of PDC-1421 Capsule and placebo thrice daily; two capsules of PDC-1421 Capsule thrice daily; two capsules of placebo thrice daily) for 42 days. After the two weeks of drug administration, subjects will return to the center for assessments then get another study drug bag for the following 14 days. The biweekly clinic visits are three times and one week later after the last dose for follow-up.

### 5.2.3 *Flowchart of study procedures*

Part I-schedule of assessments

\*On  $\pm 2$  days.

\*V3 (Week 1/2) only can be conducted in Day 3 or Day 4.

Visit	Screening		Treatment Period					Follow-up
	1	2	3	4	5	6	7	
*Week	-2 to -1 ~0	0	1/2	1	2	3	4	5
Informed consent	•							
Subject information	•							
Medical history	•	•						
DSM-IV-TR	•							
HAM-D-17	•	•		•	•	•	•	•
CGI	•	•		•	•	•	•	•
MADRS	•	•		•	•	•	•	•
DSSS	•	•		•	•	•	•	•
HAM-A	•	•		•	•	•	•	•
C-SSRS	•	•	•	•	•	•	•	•
Concomitant medication	•	•	•	•	•	•	•	•
Physical examination	•	•	•	•	•	•	•	•
Vital sign	•	•	•	•	•	•	•	•
ECG	•	•	•	•	•	•	•	•
Laboratory examination								
Drug screen	•							
Pregnancy test	•							•
Hematology	•	•			•		•	•
Blood chemistry	•	•			•		•	•
Eligibility evaluation	•							
Drug accountability		•	•	•	•	•	•	
AE/SAE evaluation			•	•	•	•	•	•

## Part II-schedule of assessments

\*On ±2 days.

\*\* If the interval of visit 1 and visit 2 is within 7 days, Hematology and Blood chemistry test of visit 2 can be skipped.

Visit	Screening	Treatment Period				Follow-up
	1	2	3	4	5	6
*Week	-2 to -1 ~ 0	0	2	4	6	7
Informed consent	•					
Subject information	•					
Medical history	•	•				
DSM-IV-TR	•					
HAM-D-17	•	•	•	•	•	•
CGI	•	•	•	•	•	•
MADRS	•	•	•	•	•	•
DSSS	•	•	•	•	•	•
HAM-A	•	•	•	•	•	•
C-SSRS	•	•	•	•	•	•
Concomitant medication	•	•	•	•	•	•
Physical examination	•	•	•	•	•	•
Vital sign	•	•	•	•	•	•
ECG	•	•	•	•	•	•
Laboratory examination						
Drug screen	•					
Pregnancy test	•					•
Hematology	•	• **	•	•	•	•
Blood chemistry	•	• **	•	•	•	•
Eligibility evaluation	•					
Drug accountability		•	•	•	•	
AE/SAE evaluation		•	•	•	•	

## 5.3 Statistical Methods Planned in the Protocol and Determination of Sample Size

### 5.3.1 Populations for analysis

The efficacy measures are conducted on the per-protocol (PP) and intent-to-treat (ITT) basis. The per protocol will be defined as (1) The drug compliance is at least 80% (2) Subjects have completed data to determine the primary endpoint. (3) Subjects cannot have protocol deviation. The protocol deviation will be defined as (1) Inclusion or exclusion criteria not satisfied. (2) Not permitted concomitant medications (3) Wrong randomized treatment prescribed. An intent-to-treat (ITT) basis will be defined as the data are analyzed by the treatment groups to which the randomized patients who take at least one dose of study medication and have any post-baseline safety data collected.

The safety measures are conducted on the ITT basis.

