3.4 Randomization and Blinding

Table 13. Summary of randomization and blinding

	Part I	Part II
Randomization	None (open label)	Randomized; 1 capsule TID: 2 capsules TID: placebo = 1:1:1
Blinding	None (open label)	Double-blind; (1) Unblinding at the end of trial (2) Emergency unblinding at a serious adverse event.

The randomization scheme generated by computer will be prepared by the CRO prior to the start of the study. In part II, subjects will be randomly allocated to the group of one of PDC-1421 Capsule (3 or 6 capsules) or placebo in a ratio of 1:1:1. All subjects and medical staff will be blinded to the treatment assigned till the end of the trial. All emergency unblinding (e.g., due to a serious adverse event) should be reported immediately to the BioLite, Inc. Codes linking randomization number to actual

treatment for each subject will be secured in a sealed, opaque envelop and maintained in the study site and research department of BioLite, Inc.

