### 6.1 Data Sets Analyzed

Two study populations are intention-to-treat (ITT) population and per-protocol (PP) populations which are defined in section 5.3.1.

The efficacy evaluations will be performed on both of the ITT and PP datasets while the safety evaluations will be performed on the ITT dataset. The primary conclusion will be made for the primary endpoint on the ITT population

Demographic and baseline (Visit 2) characteristics will be performed on the ITT population.

Sample size, mean, 95% confidence interval of mean, median, standard deviation, inter-quartile range, maximum and minimum will be summarized for continuous variables. For categorical variables, the frequency and percentage will be provided.

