### ***6.6.6 Use of An “Efficacy Subset” of Subjects***

All analyzed populations were defined in section 5.3.1; no other population will be utilized in statistical analyses.

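### Safety is tabulated on the ITT set by assigned arm with no rule for a patient given the wrong treatment, and the ITT definition conflicts with other sections over Part I

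*SAP*

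**What the plan says.** SAP 5.3.1, repeating Protocol 8.3, places safety on the intent-to-treat set: "The safety measures are conducted on the ITT basis". SAP 6.1 confirms it: "while the safety evaluations will be performed on the ITT dataset". The ITT definition in SAP 5.3.1 reads in part that "the data are analyzed by the treatment groups to which the randomized patients who take at least one dose of study medication", and adds a requirement for some post-baseline safety data. The sentence lacks its verb, but under the ITT label the natural meaning is the arm assigned at randomisation.

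The same section lists "Wrong randomized treatment prescribed" among the protocol deviations, and these matter only for membership of the per-protocol set. SAP 6.6.6 closes off alternatives: "no other population will be utilized in statistical analyses".

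On Part I, Table 13 in Protocol 3.4 shows an open-label part without randomisation. SAP 5.2, like Protocol 3.1, sets the target as "72 subjects who met the intent-to-treat (ITT) basis, in which 12 are assigned to part I, 60 are assigned to part II". It describes Part I as a safety evaluation: "Six subjects each will be evaluated for any safety concerns at 1 or 2 capsules TID dose for 28 days, sequentially".

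**The concern.** The secondary objective (Protocol 2, SAP 5.1.2) concerns safety in patients who receive the drug at different dose levels. That is a question about treatment taken, but the analysis set groups patients by treatment assigned. If a placebo patient is given active capsules and has an adverse event, the stated rule counts it as a placebo event. If the drug causes the event, such errors tend to narrow the contrast between arms, which is the less cautious direction for safety.

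The second difficulty is the word limiting ITT to randomised patients. Part I patients are never randomised, so a programmer who follows SAP 5.3.1 and one who follows SAP 5.2 would build different safety sets. A smaller consequence of the same definition is that a dosed patient with no post-baseline safety data drops out of the safety denominator.

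**Working it through.** **Inputs.** Part I has 12 patients (6 per dose) and Part II has 60, randomised 1:1:1 (SAP 5.2). Part II supply is 42 packs per two-week bag and 126 packs in all (Protocol 3.5.4).

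**The plan's ITT count.**
- Stated: 72. Reproduced: 12 + 60 = 72.
- Under the literal definition (randomised patients only): 60.
- Difference: 12 patients, or 12/72 = 16.7% of those planned to be dosed.

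**What the plan intends for Part I.**

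| Place | Treatment of Part I |
|---|---|
| SAP 5.3.1, Protocol 8.3 | ITT limited to randomised patients, so the 12 do not qualify on the words |
| SAP 5.2, Protocol 3.1 | The 12 are counted within the 72 on the ITT basis |
| SAP 6.1 with 6.2 | Baseline tables use the ITT population and are presented by part |
| SAP 6.5.1 to 6.5.7 | Adverse events, serious events, laboratory data, physical examination, vital signs, ECG and C-SSRS results are presented by part |

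Three of the four rows include Part I. The definition is the outlier.

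**Effect of one misdispensed patient.** Part II arm size is 60/3 = 20. Suppose a patient assigned to placebo takes one of the active doses throughout and has the event. Let e be the number with the event among the 20 assigned to placebo, including this patient, and f the number among the 20 assigned to that active dose.

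- Placebo: e/20 as assigned, (e − 1)/19 as received. Difference = (20 − e)/380.
- Active: f/20 as assigned, (f + 1)/21 as received. Difference = (20 − f)/420.

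The counts below are assumed for illustration; the documents give no event rates.

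| Case | As assigned | As received | Shift |
|---|---|---|---|
| Placebo, e = 1 (largest) | 1/20 = 5.0% | 0/19 = 0% | 5.0 points |
| Active, f = 0 (largest) | 0/20 = 0% | 1/21 = 4.8% | 4.8 points |
| Placebo, e = 10 | 10/20 = 50.0% | 9/19 = 47.4% | 2.6 points |
| Active, f = 4 | 4/20 = 20.0% | 5/21 = 23.8% | 3.8 points |

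For a patient who has the event, about 5 points is therefore the upper value per arm. If the misdispensed patient does not have the event, only the denominators change: with f = 4, 4/20 = 20.0% becomes 4/21 = 19.0%, a shift of 1.0 point. With no dispensing error the shift is zero.

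**Mixed exposure.** 126/42 = 3 bags per Part II patient, handed out at weeks 0, 2 and 4 (Protocol 5.2.3). One wrong bag would leave a patient exposed to two treatments, so grouping by treatment received is incomplete without a rule for that case.

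**The case against.** Four fair points can be made in favour of the plan.

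1. **Part I.** A reader might infer that the 12 Part I patients are left out of the safety analysis. The documents do not support that: the design sections count them as ITT and SAP 6.5 reports safety by part. This point stands, and it reduces the Part I issue to a wording conflict.
2. **The error is hypothetical.** Nothing in the documents reports a dispensing error. The definition sentence is also incomplete, so grouping by assigned arm is an interpretation, though the natural one. Both parts stand.
3. **An error would be visible.** A reader might infer that dose-related harm would be concealed. That goes too far. Deviations are listed and tabulated (SAP 9.3), and serious events are listed with a narrative (Protocol 8.3, SAP 5.3.3.1), so the patient could be traced. What remains is that the summary tables would still carry the event in the wrong column.
4. **Five points is not a per-patient effect.** It needs the patient to have the event, and it shrinks as the event becomes more common among the assigned patients. This stands.

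None of these supplies the missing rule. The plan names the error, gives the safety tables no way to handle it, and bars the population that would.

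**Conclusion.** The point holds as an inexpensive improvement that should be made. Safety grouped by assigned arm does not match an objective framed around treatment received. Under the stated rule, a misdispensed patient's events would be tabulated under a treatment not taken. The size is up to about 5 percentage points in an arm's event rate for one such patient who has the event, and zero if no error occurs. This assumes 20 patients per arm, a full course of the wrong treatment, and the natural reading of the incomplete ITT sentence.

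The 60-versus-72 conflict is present whether or not any dispensing error occurs, and needs reconciling. The figure of 12/72 measures how many patients the inconsistent wording touches, not how many the plan means to drop.

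**What to change.** In SAP 5.3.1 and 6.1 and in Protocol 8.3, define a safety set of all patients in either part who took at least one dose, summarised by treatment actually received. Amend SAP 6.6.6 so that this set is permitted.

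- Keep Part I and Part II in separate summaries, as SAP 6.5 already does, so that 28-day open-label patients are not pooled with 42-day blinded patients.
- State a rule for a patient who received more than one treatment across the two-week bags; for example, classify by the highest active dose received and list the case.
- Run all safety tables on this set and keep ITT for efficacy.
- Complete the ITT sentence and reconcile its restriction to randomised patients with the count of 72 in SAP 5.2 and Protocol 3.1.

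The cost is one more analysis-set definition and conforming edits in two documents. No new data are needed. If no dispensing error occurs, the Part II safety tables are essentially unchanged.

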### 5.3.2 Endpoints

#### Primary endpoint:

CONFIDENTIAL

Project No. BLI-1005-002

Statistical Analysis Plan for PDC-1421

“Final” Page 18 of 34

Protocol Version: 2.3

SAP Version: 20180626\_01

In part II, the primary endpoint is the change of Montgomery-Åsberg Depression Rating Scale (MADRS) total score from baseline to Week 6 compared to placebo.

**Secondary endpoints are:**

- MADRS total score—change from baseline to week 2 and 7
- HAM-D-17, CGI, DSSS and HAM-A—change from baseline to week 2, 4, 6 and 7
- Percentage of partial responders and responders (defined as participants with a 25-50% decrease and a  $\geq 50\%$  decrease from baseline in total score, respectively) in MADRS total score by Week 2, 4, 6 and 7
- Difference in the mean changes of MADRS, HAM-D-17, HAM-A, DSSS, CGI and C-SSRS from baseline to week 2, 4, 6 and 7 between PDC-1421 Capsule and placebo groups.

**Safety endpoints:**

- physical examination
- vital signs
- laboratory data (blood chemistry)
- ECG
- Columbia-Suicide Severity Scale (C-SSRS)
- Incidence of AE/SAE

**5.3.3 Statistical Evaluation**

Simple descriptive statistics with 95% confidence interval will be performed with data collected in this study wherever applicable. Treatment effects are evaluated based on 2-sided test with a 0.05 significant level. All data shall be tabulated and presented in the study report. The descriptive statistics will be provided. The safety and efficacy data will be analyzed using the non-parametric method.

